7.10. Dietary Change

A summary of changes in diet will be presented for the FAS, as well as the status whether the subject was on a low fat or low cholesterol diet at baseline (yes/no). Any change in diet (yes/no) will be summarized. Changes in diet will reflect any post-treatment change in fat content, cholesterol content, or cholesterol lowering foods; each will be summarized as to whether there was ever any reduction, ever any increase, or no change.

In addition a summary of whether there was ever a change in dosing for subjects who were on lipid lowering medication will be summarized.

7.11. Exploratory Biomarker Analyses

Exploratory disease-related biomarkers - which may be identified, based on emerging information from the SBC-102 development program and scientific literature - will be listed and observed values and changes and/or percent changes from baseline will be summarized at available timepoints.

7.12. Subgroup Analyses

Demographic and baseline disease characteristics and efficacy outcomes will be summarized by: age at start of infusion (<12 Years *versus* >=12 Years), gender (Male *versus* Female), baseline use of lipid-lowering medications (Yes *versus* No), genetic mutation category (Homozygous for common mutation *versus* Heterozygous for common mutation *versus* Other mutation), baseline fibrosis or cirrhosis status, and baseline ALT level (<1.5 x ULN vs >=1.5 x ULN). Efficacy outcomes and selected demographic or baseline disease characteristics will also be summarized for subjects 2-4 years old. HRQOL outcomes will not be summarized by subgroup. Adverse event summaries will be presented by age at start of infusion.

Summaries will be provided in the event that at least 5 subjects are included in each subgroup defined by a characteristic (eg. At least 5 subjects with ADA positive and ADA negative).

7.13. Additional Exploratory Analyses

Post-hoc subgroup analyses may be performed as needed.

7.14. Interim Analyses

There will be two Clinical Study Reports (CSRs) generated for study LAL-CL06:

- (1.) CSR#1 will present analyses described in the SAP, but with data accumulated for all subjects up to- and including the Week 96 Visit; and
- (2.) CSR#2 will present all analyses described in the SAP with data accumulated for all subjects over the entire study duration. This will be the final study CSR.

CSR#1 is being planned to enable the study team meet regulatory requirements. The analysis and subsequent release of CSR#1 will neither impact the operational characteristics of the overall study, nor affect the conduct of the remaining portion of LAL-CL06.

To facilitate the successful implementation of this strategy, two Data Base Locks (DBLs) are being planned: one for CSR#1 (DBL#1) and the other for CSR#2 (DBL#2). Efforts will be made to ensure that all queries related to data accrued up to – and including – Week 96 are resolved, and all eCRF pages up to – and including – Week 96 Visit are frozen except for AEs and concomitant medications reported as "Ongoing" as of DBL#1.

The proposed analyses are descriptive and no adjustments will be made for multiple comparisons or level of statistical significance due to multiple data locks/analyses.

7.15. Data Monitoring Committee

An independent Safety Committee (SC) will perform periodic reviews of aggregated safety data for study LAL-CL06 on an at least biannual basis (i.e., every 6 months) from the date of enrollment of the first subject until completion of dosing for all subjects in the study. Details of SC procedures, processes and analyses for the study are provided in an SC Charter.

9 APPENDICES

9.1 Protocol Schedule of events

Refer to the approved study protocol for a schedule of events.

9.2 Changes from Analyses Specified in the Previous Version of the SAP

Not applicable

9.3 Sample Size, Power, and Randomization

No formal sample size calculations were performed for this study; the projected enrollment is based on feasibility. Given the rarity of LAL-D, it is not expected that more than 20 subjects will be treated.

9.4 Technical Specifications for Derived Variables

9.4.1 Age

Age will be presented as the number of years between date of birth and the reference date. The following age will be computed, with reference dates indicated:

Table 5: Age and reference date

AGE	REFERENCE DATE		
Age at Enrollment	Date of Signing ICF		
 Age at First Dose of SBC-102 	Date of First Dose of SBC-102		

In cases where only the month and year are provided for a date, the day will be imputed as 15. Missing month will be imputed as June. In cases where the day and the month are missing, the date will be imputed as July 1.

The 2-4 year age group will be defined based on the date of first dose of SBC-102. Subjects whose date of first dose was on or after the subject's second birthday but prior to the subject's fifth birthday will be included in this subgroup.

9.4.2 Time to Peak ADA Titer

Time to Peak Titer (Weeks) = (Date of Peak ADA Titer - Date of First SBC-102 Infusion + 1)/7;

This derived variable will be used in the calculation of Kaplan-Meier estimate of median time to peak ADA titer (if calculable), and probability of "no titer detected" at selected timepoints.

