4.1. Changes from Analyses Specified in the Protocol

The following items are specified in the protocol and are not part of this analysis plan:

- The urinalysis summary of the change from baseline will not be summarized. However urinalysis results will be provided in the subject listings.
- The summary of the change in vital signs during and after infusion relative to pre-infusion values will not be summarized; instead, the change from baseline (defined below) to each post-baseline visit will be summarized. Given that multiple vital sign measurements are taken at each post-baseline visit, the average of the measurements within a visit will be summarized.
- At the time of this Statistical Analysis Plan (SAP) amendment, only 2 subjects have been anti-drug antibody (ADA) positive. As a result, a clarification was added that many of the ADA analyses will only be performed in the event that at least 5 subjects are ADA positive.
- The effect of sebelipase alpha on growth parameters in pediatric subjects will be evaluated among all subjects younger than 18 years old. The protocol specifies analyzing these data conditional on subjects having had manifestations of impaired growth. However, the analysis will not be limited to subjects showing signs of impaired growth.
- The AE table showing the incidence of AEs across time intervals will not be presented.
- The protocol indicates that percentages will be calculated including subjects with missing values.
 However, percentages will be based on subjects with non-missing values unless otherwise specified.

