5.1.1.7. Anti-drug Antibodies (ADAs)

Blood samples will be collected to test for antibodies to SBC-102 in plasma just prior to dosing, at Baseline and every 4 weeks until Week 12. After Week 12, ADA samples will be collected every 12 weeks and at end of study (or early withdrawal) visit, as well as after an IAR.

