7.2.9. Antidrug Antibody (ADA) Titer

A subject will be considered as having been ADA positive if the test was reactive and specific.

ADA data will be reported in the subject listings. The number and percentage of subjects who became ADA positive, and the number and percentage of subjects who were positive to neutralizing antibodies will be presented. Should at least 5 subjects be ADA-positive, then additional analyses will be performed to include: time to peak titer; ADA titer by time point; and median and peak ADA titer. Time to peak ADA titer will be analyzed by Kaplan-Meier method; if no titer is detected, time to peak titer will be censored at the date of the last visit during treatment with SBC-102.

Other exploratory analyses of the effect of ADAs on the safety of SBC-102 may also be performed as suggested by the type and amount of data available.

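### SAP 9.4.2 derives the probability of no ADA titer from time to peak titer, so subjects who are already positive but have not yet peaked are counted as having no titer

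*SAP*

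**What the plan says.** SAP 9.4.2 defines a single variable: "Time to Peak Titer (Weeks) = (Date of Peak ADA Titer - Date of First SBC-102 Infusion + 1)/7". It gives that variable two uses. One is the Kaplan-Meier median time to peak. The other is the "probability of 'no titer detected' at selected timepoints".

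SAP 7.2.9 sets the event and the censoring: "Time to peak ADA titer will be analyzed by Kaplan-Meier method; if no titer is detected, time to peak titer will be censored", the censoring date being the last visit on treatment. Neither section, nor the protocol, defines a time to first positive titer.

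Three further statements set the context:
- SAP 7.2.9 makes the analysis conditional: "Should at least 5 subjects be ADA-positive, then additional analyses will be performed". SAP 4.1 records that, at the amendment, "only 2 subjects have been anti-drug antibody (ADA) positive".
- SAP 5.1.1.7 plans sampling every 4 weeks to Week 12; then "After Week 12, ADA samples will be collected every 12 weeks".
- Protocol 3.1 has each subject treated for at least 52 and up to 96 weeks, with up to 48 more weeks in the expanded period, so follow-up can differ between subjects.

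**The concern.** The survival function of time to peak is the probability that the peak has not yet occurred. The probability that no titer has been detected is a different quantity, and its event is the first positive sample. The two agree only for subjects whose first positive sample is also their peak. For example, a subject first positive at Week 8 with a peak at Week 36 stays event-free for 28 weeks (36 − 8) and is labelled as having no titer throughout.

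Immunogenicity is a secondary objective (Protocol 2.2), and antibody incidence and titer are part of the safety assessment in SAP 5.1.1. Protocol 3.2.1.1 also singles out the relation between ADA positivity and infusion-associated reactions. A curve labelled as antibody-free that includes antibody-positive subjects would misstate when antibodies appear.

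**Working it through.** The plan states no figure for this probability, so there is nothing to reproduce. The check compares the estimate under the SAP rule (event = peak) with the estimate that fits the label (event = first positive).

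**Inputs from the documents.** Event, censoring rule and sampling are as described above. The threshold is 5 ADA-positive subjects (SAP 7.2.9). The expected number treated is no more than 20 (SAP 9.3) or about 30 (Protocol 8.2).

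**Assumed inputs.** All titer dates are assumed. Nominal weeks are used.

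**Direction before any censoring.** Both Kaplan-Meier curves are then simple proportions:

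- S_peak(t) = 1 − (number peaked by t)/N
- S_first(t) = 1 − (number positive by t)/N

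First positive never comes after peak, so S_peak(t) ≥ S_first(t). The inequality is strict when t falls after some subject's first positive sample and before that subject's peak.

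**Case A, common follow-up.** Five subjects are positive. First positives are at Weeks 4, 8, 8, 12, 24 and the matching peaks at Weeks 12, 24, 36, 48, 60. All others are never positive and censored at Week 96. For N = 20 at Week 24, S_peak = 18/20 = 0.90 and S_first = 15/20 = 0.75.

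| Week | 4 | 8 | 12 | 24 | 36 | 48 | 60 |
|---|---|---|---|---|---|---|---|
| N=20, peak (SAP rule) | 1.00 | 1.00 | 0.95 | 0.90 | 0.85 | 0.80 | 0.75 |
| N=20, first positive | 0.95 | 0.85 | 0.80 | 0.75 | 0.75 | 0.75 | 0.75 |
| Excess | 0.05 | 0.15 | 0.15 | 0.15 | 0.10 | 0.05 | 0.00 |
| N=30, peak (SAP rule) | 1.00 | 1.00 | 0.967 | 0.933 | 0.900 | 0.867 | 0.833 |
| N=30, first positive | 0.967 | 0.900 | 0.867 | 0.833 | 0.833 | 0.833 | 0.833 |
| Excess | 0.033 | 0.100 | 0.100 | 0.100 | 0.067 | 0.033 | 0.000 |

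The added day in the SAP formula moves every event 1/7 week later. Read at exactly Week 24 with N = 20, the values become 0.95 and 0.80, and the excess is still 0.15.

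**Case B, staggered follow-up, N = 20.** First positives are as in Case A. Eight never-positive subjects are censored at Week 52 and seven at Week 96. Peaks are at Weeks 12, 24, 60, 84, 96. The eight censored at Week 52 leave the risk set before the later peaks:

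- S_peak(96) = 19/20 × 18/19 × 9/10 × 8/9 × 7/8 = 0.63
- S_first(96) = 15/20 = 0.75, because every first positive precedes any censoring

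With the Case A peaks and this censoring, S_peak(60) = 16/20 × 7/8 = 0.70 against 0.75.

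**Simulation.** N = 20 with 5 positive and 2,000 data sets per scenario. First positive falls at one of the first six post-dose samples (Week 2, on the adult schedule, included), and the peak at that or any later sample within follow-up. Mean of S_peak − S_first:

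| Follow-up (weeks) | Wk 4 | Wk 24 | Wk 36 | Wk 60 | Wk 96 | Wk 120 | Wk 144 |
|---|---|---|---|---|---|---|---|
| all to 96 | 0.071 | 0.144 | 0.155 | 0.093 | 0.000 | – | – |
| 96 to 144 | 0.073 | 0.154 | 0.169 | 0.118 | 0.045 | −0.001 | −0.041 |
| 52 to 144 | 0.071 | 0.143 | 0.153 | 0.090 | 0.011 | −0.035 | −0.073 |

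No data set gave a value below the first-positive estimate through Week 60. That follows from the set-up: the first sampling visit after Week 52 is Week 60, so nobody is censored before then. Case B shows that earlier censoring can reverse the sign by Week 60.

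**The case against.** The strongest reply is that little depends on this number. It is produced only if at least 5 subjects are ADA-positive, and 2 were at the amendment, so it may never be reported. The number and percentage who become ADA-positive, the neutralizing-antibody counts and the subject listings are produced regardless and are unaffected. If the threshold is met, titer by time point is also shown, which reveals positivity visit by visit. All analyses are descriptive (SAP 7). This all stands and limits the consequence. It does not make the estimate valid when it is run.

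A second reply concerns direction and size, and it also stands. A reader might infer that the reported probability is always too high, or that a particular overstatement can be predicted. The documents support neither. Only never-positive subjects are censored, so late peaks can fall on a depleted risk set and pull the curve below the correct value. The timepoints are left open, and no titer dates are given.

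A reader might also take the censoring of never-positive subjects as the fault. It is not: an analysis of time to first positive censors the same people. Nor is Kaplan-Meier for time to peak itself the error. Changing that summary is a matter of choice.

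**Conclusion.** The point holds as a mismatch between variable and label. SAP 9.4.2 and 7.2.9 together specify an estimate that counts antibody-positive subjects as having no titer until they peak.

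The error is upward at early and middle timepoints whenever peak follows first positive. On the assumed dates it is up to 0.15 with 20 subjects and 0.10 with 30. It can turn downward at late timepoints under staggered follow-up, by 0.12 at Week 96 in the assumed case (0.75 − 0.63). It is zero if every peak is the first positive sample, and also once all positives have peaked under common follow-up. The mismatch follows from the text alone; every size rests on assumed titer dates. Label: wrong as written.

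**What to change.** In SAP 9.4.2, add a second derived variable: time from first infusion to first positive ADA titer. In 9.4.2 and 7.2.9, state that never-positive subjects are censored for it at their last on-treatment ADA sample, and that this variable alone supplies the no-titer probabilities. Name the timepoints at which they are reported.

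Keep time to peak only for its own summary. Giving it as median, quartiles and range among ADA-positive subjects is optional. One reason to prefer that: with 5 of 20 positive and common follow-up, the peak curve stops at 0.75, so the Kaplan-Meier median is not reached.

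The cost is one derived variable and a few lines of SAP text. The samples are already collected, and no other ADA output changes.

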9.4.3 Body Mass Index (BMI)

BMI is calculated as:

BMI = body weight (Kg) / $[Height (m)]^2$

BMI is expressed in Kg/m²

9.4.4 Derivation of Study Day

The date and time of first study drug infusion is the reference day for deriving study day, and will be calculated as follows:

- for measurements on or after first study drug infusion, study day is:
 - o collection date first study infusion date + 1.
- for measurements prior to first study drug infusion, study day is:
 - o collection date first infusion date -1.
- for measurements on the day of first study drug infusion starting at the same time or after first study infusion, study day is:
 - o "Day 1".
- for measurement on the day of first study drug infusion starting prior to the first study infusion, study day is:
 - o "Day 0".

9.4.5 Definition of Baseline Values and Change from Baseline

9.4.5.1 Baseline

Baseline is defined as the last available pre-first study dose assessment for all subjects. In case of multiple pre-treatment measurements, Baseline is the average of the last (up to 3) measurements.

For laboratory parameters if any Baseline test is done at local and central laboratory, then the central laboratory results will be used for analysis.

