5.5. Physical Examination

A complete, age-appropriate physical examination will be performed by the Investigator or qualified designee, at the time points specified in [Appendix B](#). The examination will include an assessment of the subject's general appearance, skin, head (including head circumference for children up to 3 years of age), eyes, ears, nose, throat, heart, lungs, abdomen, extremities/joints, and neurological status. Whenever possible, the same person should perform the physical examination at each study visit. Abnormal findings will be recorded in the eCRF.

Every physical examination will also include the following:

- Child-Pugh Score (see [Appendix A](#));
- Abdominal photograph for subjects < 4 years of age at Screening;
- Liver size: A clinical assessment of liver size (palpable/non palpable and centimeters below costal margin), regularity (smooth/nodular), and sensitivity (tender/nontender);
- Spleen size: A clinical assessment of spleen size (palpable/nonpalpable and centimeters below costal margin), regularity (smooth/nodular), and sensitivity (tender/nontender);
- Lymphadenopathy: An assessment of the size, location, and character of any palpable lymph nodes. Areas to be examined include cephalic (occipital, preauricular, postauricular, submental, submandibular), cervical, clavicular, axillary, and inguinal. Any enlarged nodes will be characterized as tender or nontender;
- Arterial disease: A clinical assessment of the right and left posterior tibialis and dorsalis pedis pulses and carotid bruits;
- Skin manifestations: A clinical assessment of signs of liver disease and portosystemic anastomoses such as periumbilical venous engorgement (caput medusae), spider nevia, or gynecomastia, dylipidemia such as xanthomas (tendinous, tuberos) and xanthelasma, and allergies including assessment of allergic skin rashes.

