Appendix A: Child-Pugh Score and Classification

The Child-Pugh score is calculated as the sum of the individual scores for each of the following 5 factors:

| Parameter | | Score | | |
|---------------------------------------|-------------------|---------|-------------------|-------------------|
| | | 1 Point | 2 Points | 3 Points |
| Total Serum Bilirubin | mg/dL | <2.0 | 2.0 to 3.0 | >3.0 |
| | µmol/L | <34 | 34 to 51 | >51 |
| Serum Albumin | g/dL | >3.5 | 3.0 to 3.5 | <3.0 |
| | g/L | >35 | 30 to 35 | <30 |
| Prothrombin Time | Seconds prolonged | 0 to 4 | 4 to 6 | >6 |
| | INR | <1.7 | 1.7 to 2.3 | >2.3 |
| Ascites | | None | Easily controlled | Poorly controlled |
| Hepatic Encephalopathy | | None | Minimal | Advanced |
| INR = International Normalized Ratio | | | | |
| Source: Harrison's Manual of Medicine | | | | |

The Child-Pugh classification is then determined as follows:

| Child-Pugh Classification | Total Child-Pugh Score |
|---------------------------|------------------------|
| Class A | 5 to 6 |
| Class B | 7 to 9 |
| Class C | 10 to 15 |

Appendix B: Schedules of Assessments**Schedule I - Assessments for Adult Subjects (Subjects ≥18 years) - Screening to Week 48 of Treatment Period**

| Assessments* | Screening | Treatment | | | | | | | | | | | | | |
|---|------------------|----------------|------------------------------|----------------|----------------|----------------|----------------|----------------|----------------|----------------|----------------|----------------|----------------|----------------|----------------|
| | Day -45 to Day 0 | Day 0 | Week 2 | Week 4 | Week 8 | Week 12 | Week 16 | Week 20 | Week 24 | Week 28 | Week 32 | Week 36 | Week 40 | Week 44 | Week 48 |
| | | | ±7 days | ±7 days | ±7 days | ±7 days | ±7 days | ±7 days | ±7 days | ±7 days | ±7 days | ±7 days | ±7 days | ±7 days | ±7 days |
| Informed Consent/Assent | X | | | | | | | | | | | | | | |
| Inclusion/Exclusion Criteria | X | X ^p | | | | | | | | | | | | | |
| Medical History | X | | | | | | | | | | | | | | |
| AUDIT | X | | | | | | | | | | | | | | |
| Historical DNA Results ¹ | X | | | | | | | | | | | | | | |
| 12-lead ECG | X | | | | | | | | | | | | | | X ^p |
| Physical Examination ² | X | X ^p | | | | X ^p | | | X ^p | | | X ^p | | | X ^p |
| Height | | X ^p | | | | | | | | | | | | | |
| Weight | | X ^p | Every two weeks ^p | | | | | | | | | | | | |
| Abdominal MRI ³ | X | | | | | | | | | | | | | | X ^p |

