7.2.4. Child-Pugh Status

Using the Total Child-Pugh score, subjects will be classified into categories A (score 5 to 6), B (score 7 to 9), and C (score 10 to 15). Higher scores and higher categories represent a worse outcome.

Total Child-Pugh scores will be summarized as a continuous endpoint showing the observed values at baseline and each post-baseline visit, as well as the change from baseline and the percent change from baseline to each post-baseline visit. This summary will be presented for those subjects with a Class B or C at baseline as well as for all subjects in the FAS.

The number and percentage of subjects in each of the categories (A, B, and C) will be summarized for each visit at which the test was performed. In addition a shift from baseline will be presented showing improvement, no change, and decline. Generally, percentages will be based on the number of subjects with baseline and post-baseline results. However, percentages for shifts of improvement (i.e., B to A, C to B, and C to A) will be based on subjects who had scores of B or C at baseline. Similarly, percentages for shifts of worsening (i.e., A to B, A to C, and B to C) will be based on subjects who had scores of A or B at baseline.

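### The SAP's baseline averaging rule has no exception for ordinal or categorical variables, so a Child-Pugh baseline can be 6.5 or 9.5 and fall in no class

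*SAP*

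**What the plan says.** SAP 9.4.5.1 first states: "Baseline is defined as the last available pre-first study dose assessment for all subjects". It then adds: "In case of multiple pre-treatment measurements, Baseline is the average of the last (up to 3) measurements". SAP 7.2, the safety section that contains the Child-Pugh analysis, repeats the averaging sentence. Neither place limits averaging to a type of variable.

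Protocol 5.5 introduces a list of items with "Every physical examination will also include the following", and the Child-Pugh score is the first item. Both schedules in Protocol Appendix B (adult and pediatric) place a physical examination at Screening and another before the infusion on Day 0.

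Protocol Appendix A builds the total: "The Child-Pugh score is calculated as the sum of the individual scores for each of the following 5 factors". Each factor earns 1, 2 or 3 points. In SAP 7.2.4, "subjects will be classified into categories A (score 5 to 6), B (score 7 to 9), and C (score 10 to 15". That section gives no separate Child-Pugh baseline and no rounding rule. Baseline class then decides three things there:

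- who enters the total-score summary restricted to baseline class B or C;
- the denominator for improvement (baseline B or C);
- the denominator for worsening (baseline A or B).

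SAP 5.2.1 and Protocol 3.2.1.2 list a fall in Child-Pugh status among subjects in class B or C at baseline as an efficacy endpoint. SAP 7.2.5 tabulates palpable or not, smooth or nodular, and tender or not, for liver and spleen at baseline.

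**The concern.** Averaging suits ALT or blood pressure. It does not suit a score whose only use in a shift table is to be sorted into whole-number bands, and it has no meaning for a yes/no finding. Two pre-dose examinations are scheduled, so the averaging rule can be triggered by an ordinary visit pattern and does not need an unusual one.

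When the average lands between bands, a programmer who follows the SAP exactly has no class to assign. The subject is then dropped, rounded up, rounded down or set to the last value, and each choice can give a different shift table. The choice would be made in an open-label study with post-baseline data in hand, on a secondary endpoint with small denominators. The subjects at risk sit at a class boundary, and severe liver disease is one of the target groups in Protocol 4.1.

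**Working it through.** There is no sample size figure to reproduce here (SAP 9.3: "No formal sample size calculations were performed for this study; the projected enrollment is based on feasibility"). The figures to check are the class bands.

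**1. Single-visit totals.** Five factors at 1 to 3 points give totals from 5 × 1 = 5 to 5 × 3 = 15, which is 11 integers. The bands 5–6, 7–9 and 10–15 place every one in exactly one class, so the classification works for a single assessment.

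**2. Mean of two totals.** A mean falls in no class if it lies strictly between 6 and 7 or between 9 and 10. For two integers this means 6.5 (sum 13) or 9.5 (sum 19).

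- One-point differences: (6 + 7)/2 = 6.5; (9 + 10)/2 = 9.5.
- Sum 13 from totals of 5 to 15: (5,8), (6,7), so 2 pairs.
- Sum 19: (5,14), (6,13), (7,12), (8,11), (9,10), so 5 pairs.
- In all, 7 of the 66 unordered pairs have no class.

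**3. Mean of three totals** (only if an extra pre-dose assessment occurs). Enumeration gives 44 of 286 unordered triples with no class, at 6.33, 6.67, 9.33 or 9.67.

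These counts show what is possible. They are not expected frequencies.

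**4. Can the score move between Screening and Day 0?** In both schedules the liver panel (bilirubin, albumin) is drawn at both visits, but the coagulation panel is drawn at Screening and not on Day 0. Holding PT/INR at its Screening value, take bilirubin 1, albumin 1, PT 1, ascites 2, encephalopathy 1 = 6. If albumin moves to 2 points, the total is 7 and the mean is 6.5. A straddling pair therefore does not need a second INR.

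**5. What is undefined at each value.**

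- At 6.5 (between A and B): membership of the B/C subset and of the improvement denominator. The shift label is also open, since a later class B is worsening from A but no change from B.
- At 9.5 (between B and C): the subject belongs to B/C either way and stays in the improvement denominator. The place in the worsening denominator is open, and so is the shift, since a later class B is improvement from C but no change from B.

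**6. Effect on the improvement rate.** The documents do not give the number n of baseline class B/C subjects. Let k be the number who improve.

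- Dropping a 6.5 subject who improved: k/n becomes (k − 1)/(n − 1), a change of (n − k)/[n(n − 1)].
- Dropping one who did not improve: k/n becomes k/(n − 1), a change of k/[n(n − 1)].
- Labelling a 9.5 subject B or C: a change of 1/n if the later class is B, otherwise 0.

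The ceiling is 1/n in each case. With an assumed n = 5, 1/5 to 0/4 is 20 points, 3/5 to 2/4 is 10 points and 5/5 to 4/4 is 0, so the range is 0 to 20 points. With an assumed n = 10 the ceiling would be 1/10, or 10 points.

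**7. Last single score instead.** 6 then 7 gives class B, and 9 then 10 gives class C. Every baseline is an integer from 5 to 15 and has one class.

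**The case against.** The strongest reply is that the two sentences in SAP 9.4.5.1 are a general rule and a special case, and that the special case concerns numeric measurements. Where the SAP applies it explicitly (7.2.6), it is to vital signs. A category cannot be averaged, so the first sentence would supply its baseline, and nobody would be left unclassified. The first part stands: a reader might infer that the SAP contradicts itself, and it does not. The rest does not rescue Child-Pugh. The total is numeric, SAP 7.2.4 summarises it as a continuous endpoint, and the class is derived from that total. For examination findings the reading is sensible but unwritten. SAP 7.2.5 mentions both Screening and baseline without saying which pre-dose visit supplies the baseline.

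A second reply is that no complete, independent Day 0 score is scheduled, because PT/INR is missing on that day. This stands as a limit. A reader might infer that every subject has two scores and that averaging always applies. The documents do not establish that, because they do not say whether the Screening PT/INR is carried forward or the Day 0 score is incomplete. If it is incomplete, only the Screening score remains.

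Third, ECG interpretation and liver histology might seem to share the problem. Each has one scheduled pre-dose assessment, so as scheduled they do not.

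Finally, the study is descriptive with no formal testing, and all data are listed by subject, so an affected subject would be visible. That lowers the stakes but does not tell the programmer what to do.

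**Conclusion.** The point holds. This is more than missing detail: applying the stated rule to scheduled assessments can produce a Child-Pugh baseline that the SAP's own classes do not cover, and it cannot be applied to discordant categorical findings.

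It affects only subjects whose pre-dose scores differ across a class boundary and average to a value between bands. How many there will be cannot be estimated from the documents. The 20-point figure might be read as the expected effect, but it is the ceiling under an assumed 5 class B/C subjects, and the change can be zero. Small denominators are realistic, since SAP 9.3 expects no more than 20 treated subjects and Protocol 8.2 about 30. Because baseline class defines the population of a secondary endpoint, this should be settled before database lock, but it does not threaten the study's primary safety objective.

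**What to change.** In SAP 9.4.5.1 and 7.2:

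- Limit averaging of up to three pre-dose values to continuous measures (laboratory values and vital signs).
- For Child-Pugh class and the categorical examination findings, take the last complete pre-dose assessment as baseline. Take the Child-Pugh total from the same assessment, so that score and class agree.
- State how the missing Day 0 PT/INR is handled: either the Screening PT/INR is used to complete the Day 0 score, or the Screening score is the baseline.
- Apply the same last-value rule to ECG interpretation and histology only if an extra pre-dose assessment occurs.

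The cost is a short clause in two places and one sentence on PT/INR, with no new data collection. There is a small downside. The Child-Pugh baseline then rests on a single visit, and it may not match the averaged bilirubin and albumin baselines reported beside it. A table footnote can say so.
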